4. STUDY DESIGN

4.1. Overall Design

The study is being conducted as a randomized, 2-period, 2-sequence, cross-over study to determine the effect of a single dose of ALXN1840 (perpetrator) on the single dose bupropion (victim) kinetics in healthy male and female participants.

The study has a Screening period (Day -28 to Day -2), two 11-day study periods (Day 1 to Day 11) with a minimum of 14 days between doses of bupropion, and an End of Study (EOS) Visit (Day 15 ± 2 days) after Period 2 dosing. Participants will report to the clinical research unit (CRU) on the day prior (Day -1) to both dosing periods.

All participants will receive 1 treatment in each study period; treatment order will be defined based on randomization:

- Treatment A: One 150 mg bupropion HCl salt tablet (WELLBUTRIN SR 150) with 240 mL water (fasting).
- **Treatment B**: One 150 mg bupropion HCl salt tablet (WELLBUTRIN SR 150) + 4×15 mg ALXN1840 EC tablets with 240 mL water (fasting).

Based on randomization, participants will be administered either Treatment A or Treatment B in each period. A wash-out period of at least 14 days must separate dose administration in Period 1 and Period 2. Participants will remain institutionalized from the day prior to dosing until Day 11 following dose administration for each period.

The PK profile of ALXN1840 and bupropion will be determined by blood sampling following single dose administration over approximately 5 half-lives or more for both study interventions. Blood sampling for PK assessments will occur at pre-dose, 1, 2, 3, 4, 5, 6, 8, 12, 24, 48, 72, 96, 120, 144, 168, 192, 216, 240, and 336 hours post-dose to ensure full assessment of exposure over time. The nominal 336-hour sample for Period 1 is pre-dose sample for Period 2. In addition to PK sampling, safety and tolerability will be assessed by monitoring AEs, vital signs, 12-lead electrocardiograms (ECGs), and laboratory parameters.

Following scheduled procedures on Day 11, participants will be discharged from the unit. If there are any participants with clinically significant abnormalities at the time of discharge, the Investigator should notify the Medical Monitor prior to discharge, and participants may be asked to remain institutionalized for further clinical monitoring.

Participants may be asked or required to stay in the CRU between Periods 1 and 2, and/or before the EOS visit, for their own safety, and also to maintain the integrity of the conduct of the study.

The End of Study (EOS) Visit will occur approximately 4 days after discharge from Period 2 after collection of the nominal 336-hour PK sample.

This study will include approximately 52 participants to complete at least 32 participants.

Participants will be randomized to one of two sequences as described in Table 3.

Table 3: Study Design

Sequence number	Treat	Total	
	Study Period 1	Study Period 2	
1	A	В	26
2	В	A	26
Total			52

Treatment A - One 150 mg bupropion HCl salt tablet (WELLBUTRIN SR 150) with 240 mL water (fasting) Treatment B - One 150 mg bupropion HCl salt tablet (WELLBUTRIN SR 150) $+ 4 \times 15$ mg ALXN1840 enteric-coated tablets with 240 mL water (fasting)

At the Investigator's discretion, additional participants may be screened to allow for a full enrollment of the study; therefore, it is possible that all eligible participants may not be included. Participants not included in the study will be discharged without dosing on Day 1.

4.2. Scientific Rationale for Study Design

This study is being conducted in healthy participants so that the assessments are not confounded by disease activity, comorbidities, or concomitant medications. The inclusion and exclusion criteria for this study are consistent with Phase 1 clinical pharmacology studies that assess the medication of interest and to minimize assignment bias.

A 2-way crossover study design was adopted to control the variability within and between participants. Given the desire to evaluate the impact of sequence of administration, the study is being conducted as a 2-sequence, 2-period cross-over study. Blood sampling for PK assessment will include measures for ALXN1840 and bupropion. Blood sampling timepoints support evaluation of time to reach maximum observed plasma concentration (T_{max}) and T_{max} and include a minimum of 5 half-lives between each study intervention.

The interval between dose administration in each period will be at least 14 days, based on the estimated mean half-life for ALXN1840 of approximately 2 days as previously reported in the bioavailability studies (Studies WTX101-101 and WTX101-102), where healthy participants took an oral dose at 60 mg. Therefore, a minimum of 14 days between dose administration is considered sufficient to eliminate, on average, approximately more than 99.2% of the plasma total Mo before a second dose of bupropion. The approximately 4-day interval after Period 2 dose administration will also ensure that the participants will have eliminated measurable concentrations of ALXN1840 at the EOS Visit regardless of the randomized dosing sequence. The mean elimination half-life (\pm SD) of bupropion after chronic dosing is 21 (\pm 9) hours, therefore a minimum of 14-day interval between single dose administrations is sufficient to eliminate greater than 99.2% of plasma bupropion.

4.3. Justification for Dose

ALXN1840

The maximum tolerated dose (MTD) of ALXN1840 is unknown. To date, the 60 mg single dose and repeated daily doses have shown a good safety profile and were well tolerated throughout the Phase 1 to Phase 3 clinical studies. The 60 mg dose is well within the dose range demonstrated to have a good safety profile in studies in healthy volunteers and patients with WD. The 60 mg dose is well within the dose range to have an acceptable safety profile in humans as

demonstrated in the completed bioavailability studies that were conducted in healthy male and female participants (Study WTX101-101 and Study WTX101-102) with a median (range) body weight of 80.8 kg (57.6 to 107.0 kg) as well as the completed Study WTX101-201, conducted in patients with WD.

Tetrathiomolybdate reacts with albumin-bound Cu in the liver or blood to form a stable tripartite complex which is excreted into the bile. Tetrathiomolybdate which does not bind to Cu and albumin, is not metabolized by the liver but undergoes hydrolysis to form molybdate anion, which is excreted in the urine. Therefore, findings from the human microsome study (Study CYP0840-R2) are considered an over-estimation of the effect to be observed in vivo. Given that in vitro inhibition was observed with the ALXN1840 parent drug and no apparent accumulation of free ALXN1840 as part of the plasma ultrafiltrate (PUF) Mo or non-TPC-bound Mo after ALXN1840 repeated dosing (preliminary results from Study WTX101-201), a single dose of ALXN1840 is considered to be sufficient to assess the inhibition potential of CYP2B6 using bupropion as the substrate. Single dose administration of the ALXN1840 tablet under fasted conditions resulted in a peak drug concentration of total Mo at approximately 4.54 hours, with a half-life of approximately 51 hours (Study WTX101-102).

Bupropion

Bupropion is extensively metabolized in humans. Following oral administration of 150 mg of 14C-bupropion in humans, 87% and 10% of the radioactive dose were recovered in the urine and feces, respectively. The fraction of the oral dose of bupropion excreted unchanged was only 0.5%, a finding consistent with the extensive metabolism of bupropion (WELLBUTRIN SR).

In humans, following oral administration of WELLBUTRIN SR tablet, peak plasma bupropion concentrations are usually achieved within 3 hours, followed by a biphasic decline. The terminal phase has a mean half-life of 14 hours, with a range of 8 to 24 hours. The mean elimination half-life (\pm SD) of bupropion after chronic dosing is 21 (\pm 9) hours, and steady-state plasma concentrations of bupropion are reached within 8 days. Plasma bupropion concentrations are dose-proportional following single doses of 100 to 250 mg.

Three metabolites have been shown to be active: hydroxybupropion, formed via hydroxylation of the tert-butyl group of bupropion, and the amino-alcohol isomers threohydrobupropion and erythrohydrobupropion, which are formed via reduction of the carbonyl group. In vitro findings suggest that cytochrome P450IIB6 (CYP2B6) is the principal isoenzyme involved in the formation of hydroxybupropion, while cytochrome P450 isoenzymes are not involved in the formation of threohydrobupropion. Oxidation of the bupropion side chain results in the formation of a glycine conjugate of meta-chlorobenzoic acid, which is then excreted as the major urinary metabolite. Because bupropion is extensively metabolized, there is the potential for drug-drug interactions, particularly with those agents that are metabolized by the cytochrome P450IIB6 (CYP2B6) isoenzyme. Following a single dose in humans, peak plasma concentrations of hydroxybupropion occur approximately 6 hours after administration of WELLBUTRIN SR tablets. Peak plasma concentrations of hydroxybupropion are approximately 10 times the peak level of the parent drug at steady state. The elimination half-life of hydroxybupropion is approximately 20 (\pm 5) hours, and its AUC at steady state is about 17 times that of bupropion. The times to peak concentrations for the erythrohydrobupropion and threohydrobupropion metabolites are similar to that of the hydroxybupropion metabolite. However, their elimination

half-lives are longer, 33 (\pm 10) hours and 37 (\pm 13) hours, respectively, and steady-state AUCs are 1.5 and 7 times that of bupropion, respectively.

Even though ALXN1840 is considered theoretically and conservatively to have potential for moderate inhibition of CYP2B6 in vitro. A dose of 150 mg is not expected to result in sufficiently high exposure to cause an increase in safety risk.

4.4. End of Study Definition

A participant is considered to have completed the study if he/she has completed all phases of the study including the last scheduled procedure shown in the Schedule of Activities (SoA).

The end of the study is defined as the date the last participant completes the last visit as shown in the SoA (Table 1).

5. STUDY POPULATION

Prospective approval of protocol deviations to recruitment and enrollment criteria, also known as protocol waivers or exemptions, is not permitted.

5.1. Inclusion Criteria

Participants are eligible to be included in the study only if all of the following criteria apply:

Age

1. Participants must be 18 to 50 years of age inclusive, at the time of signing the informed consent.

Type of Participant and Disease Characteristics

- 2. Participants who are healthy as determined by medical evaluation including medical history, physical examination, vital signs, 12-lead ECG, and clinical laboratory evaluation (hematology, biochemistry, coagulation, and urinalysis) that are reasonably likely to interfere with the participant's participation in or ability to complete the study, or to potentially confound interpretation of study results, as assessed by the Investigator.
- 3. Adequate venous access in the left or right arm to allow collection of a number of blood samples.

Weight

4. Body weight \geq 45 to \leq 100 kg and body mass index (BMI) within the range of 18 to < 30 kg/m² at Screening.

Sex

- 5. Contraceptive use by men or women should be consistent with local regulations regarding the methods of contraception for those participating in clinical studies.
 - a. Male Participants:
 - Male participants, if heterosexually active with a female spouse or partner of childbearing potential or a pregnant or breastfeeding spouse or partner, must agree to use barrier contraception (male condom) for the duration of the study and for at least 3 months after the end of systemic exposure of the study intervention (ie, 3 months after the EOS Visit). Male participants must also agree to not donate sperm for at least 3 months after the end of systemic exposure of the study intervention (ie, 3 months after the EOS Visit).
 - Female spouses or partners of male participants who are of childbearing potential must use highly effective contraception as defined below and in Section 10.4, starting at least 1 menstrual cycle before (the male participant's) first study intervention administration and continuing until at least 3 months after the end of their male partner's systemic exposure to the study intervention (ie, 3 months after the EOS Visit).
 - Barrier contraception is required even with documented medical assessment of surgical success of a vasectomy. For male participants who have had a vasectomy

(with documented evidence of azoospermia if possible) and agree to use a barrier method (male condom) for the stated time period, no additional contraceptive method is required by their female partner.

- b. Female Participants:
- Female participants or female partners of male participants of childbearing potential (including breastfeeding females), if heterosexually active, must be willing to follow protocol-specified contraception guidance starting at least 1 menstrual cycle before first study intervention administration and continuing for at least 3 months after the end of systemic exposure of the study intervention (ie, 3 months after the EOS Visit). Female participants must not donate ova for at least 3 months after the EOS (ie. 3 months after the EOS Visit).
- Female participants who are documented as being of non-childbearing potential as defined in Section 10.4 are exempt from contraception requirements.
- Highly effective contraceptive methods for female participants and female partners of male participants are described in Section 10.4.
- Women of childbearing potential must have a negative highly sensitive serum pregnancy test at screening. Additional urine pregnancy testing will be standard for the protocol unless serum testing is required by site policies, local regulation, or IRB/IEC and should be performed per the time points specified in the SoA (Table 1:

Informed Consent

6. Capable of giving signed informed consent as described in Section 10.1.3, which includes compliance with the requirements and restrictions listed in the informed consent form (ICF) and in this protocol.

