2.3.2. Benefit Assessment

This is a healthy volunteer study, and there is no direct benefit to study participants.

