10.3.1. Definition of AE

AE Definition

- An AE is any untoward medical occurrence in a participant, temporally associated with the use of study intervention, whether or not considered related to the study intervention.
- Note: An AE can therefore be any unfavorable and unintended sign (including an abnormal laboratory finding), symptom, or disease (new or exacerbated) temporally associated with the use of study intervention.

Events Meeting the AE Definition

- Any abnormal laboratory test results (hematology, clinical chemistry, or urinalysis) or other safety assessments (eg, ECG, radiological scans, vital signs measurements), including those that worsen from baseline, considered clinically significant in the medical and scientific judgment of the Investigator.
- Exacerbation of a chronic or intermittent pre-existing condition including either an increase in frequency and/or intensity of the condition.
- New conditions detected or diagnosed after study intervention administration even though it may have been present before the start of the study.
- Signs, symptoms, or the clinical sequelae of a suspected drug-drug interaction.
- Signs, symptoms, or the clinical sequelae of a suspected overdose of either study intervention or a concomitant medication. Overdose per se will not be reported as an AE/SAE unless it is an intentional overdose taken with possible suicidal/self-harming intent. Such overdoses should be reported regardless of sequelae.

Events Not Meeting the AE Definition

- Medical or surgical procedure (eg, endoscopy, appendectomy): The condition that leads to the procedure is the AE. Situations in which an untoward medical occurrence did not occur (eg, hospitalization for elective surgery if planned before the signing the ICF, admissions for social reasons or for convenience).
- Anticipated day-to-day fluctuations of pre-existing disease(s) or condition(s) present or detected at the start of the study that do not worsen.
- A medication error (including intentional misuse, abuse, and overdose of the product) or use other than what is defined in the protocol is not considered an AE unless there is an untoward medical occurrence as a result of a medication error.
- Cases of pregnancy that occur during maternal or paternal exposure to study intervention are to be reported within 24 hours of Investigator/site awareness. Data on fetal outcome and breastfeeding will be collected for regulatory reporting and safety evaluation.

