Note: Periodic abstinence (calendar, symptothermal, post-ovulation methods), withdrawal (coitus interruptus), spermicides only, and lactational amenorrhoea method (LAM) are not acceptable methods of contraception for this study. Male condom and female condom should not be used together (due to risk of failure with friction)

- Collection of pregnancy information
 - If a female participant or a male participant's female spouse/partner becomes pregnant during the conduct of this study, the Investigator must submit the "Pregnancy/Breastfeeding Reporting and Outcome Form" to Alexion Global Drug Safety (GDS) via fax or email (see Section 10.3 [Appendix 3] for contact information). When the outcome of the pregnancy becomes known, the form should be updated and submitted to Alexion GDS. If additional follow up is required, the Investigator will be requested to provide the information.
 - Exposure of an infant to an Alexion product during breastfeeding must also be reported (via the "Pregnancy/Breastfeeding Reporting and Outcome Form") and any AEs experienced by the infant must be reported to Alexion GDS or designee via email or facsimile (see Section 10.3 for contact information).

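### The listed eligibility criteria do not exclude breastfeeding participants, and the protocol sets no rule on feeding an infant

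*Protocol*

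**What the plan says.** Breastfeeding appears twice in the eligibility criteria (Protocol Section 5.1), both times in a contraception rule.

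- Criterion 5a, for men, sets the condom requirement: "Male participants, if heterosexually active with a female spouse or partner of childbearing potential or a pregnant or breastfeeding spouse or partner".
- Criterion 5b, headed for female participants, applies the contraception guidance to "Female participants or female partners of male participants of childbearing potential (including breastfeeding females), if heterosexually active".

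The exclusion list in Section 5.2 mentions neither breastfeeding nor lactation.

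Outside eligibility, the protocol deals with breastfeeding only once exposure may have happened. Section 10.4 states that "Exposure of an infant to an Alexion product during breastfeeding must also be reported", and Section 10.3.1 that "Data on fetal outcome and breastfeeding will be collected for regulatory reporting and safety evaluation".

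Other reproductive risks get explicit rules. Criterion 5b requires a negative serum pregnancy test at screening and contraception until 3 months after the End of Study visit, and adds that "Female participants must not donate ova for at least 3 months after the EOS".

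**The concern.** Section 6.3 ties enrolment to meeting every inclusion criterion and no exclusion criterion, so the two lists decide who may be dosed. If they are silent on nursing, a healthy breastfeeding woman meets them. She would take an investigational copper-binding agent once and bupropion twice in a trial about which Section 2.3.2 says: "This is a healthy volunteer study, and there is no direct benefit to study participants". Her infant would have no benefit either and cannot consent.

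The protocol bars ova donation and requires contraception for 3 months after the End of Study visit, yet sets no rule of any duration on feeding a child. What is at stake is avoidable exposure of a third party. The bupropion comparison itself is not in question.

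**Working it through.** There is no planned figure to reproduce. The main check is a reading of every place where a restriction could stand.

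| Place | What it says on breastfeeding |
|---|---|
| Protocol 5.1, criteria 1 to 6 | Named in 5a (partners) and 5b; contraception only |
| Protocol 5.2, criteria 1 to 21 | Nothing |
| Protocol 5.3, Table 4 (lifestyle) | Nothing |
| Protocol 7.1 (discontinuation) | Nothing; pregnancy is listed |
| Protocol 8.2.6 (pregnancy) | Nothing |
| Protocol 10.2 (laboratory tests) | Nothing |
| Protocol 10.3.1 (AE definition) | Data collected |
| Protocol 10.4 (Appendix 4) | Infant exposure and infant AEs reported; lactational amenorrhoea not accepted as contraception |
| SAP | Nothing |

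Count of criteria that exclude a breastfeeding participant: 0 of 6 inclusion and 0 of 21 exclusion. Refusing lactational amenorrhoea as a contraceptive method does not exclude a lactating woman.

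The second check is how far confinement limits exposure. Section 4.1 says "Participants will remain institutionalized from the day prior to dosing until Day 11 following dose administration for each period", and the Schedule of Activities places Day 11 at 240 hours. Assuming mono-exponential decline, the fraction left in the mother's plasma is 2^(-t / half-life), with half-lives from Section 4.3:

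- Total molybdenum, half-life about 51 h: 240 / 51 = 4.71 half-lives, leaving 3.8%. Counted from the peak at 4.54 h, 235.46 / 51 = 4.62 half-lives, leaving 4.1% of peak.
- Bupropion: "The terminal phase has a mean half-life of 14 hours, with a range of 8 to 24 hours". At the long end, 240 / 24 = 10 half-lives, leaving 0.098%. At the mean, 240 / 14 = 17.1 half-lives, leaving 0.0007%.
- Threohydrobupropion, the longest-lived active metabolite, 37 h: 240 / 37 = 6.5 half-lives, leaving about 1.1%.

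These are fractions of the mother's plasma level, not of a dose to an infant. The documents give no data on transfer of either drug into milk. Section 2.1 also says that 90% to 95% of total plasma molybdenum is bound to copper and albumin, so the 4% is not a level of free drug. The figures show only that little remains in the mother's plasma at discharge. They do not cover milk expressed inside the unit and fed to a child, a possibility that the protocol neither describes nor rules out.

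**The case against.** The strongest reply is that the protocol is not the only safeguard. Criterion 6 makes compliance with the restrictions in the consent form part of eligibility, and that form may already bar nursing women. The investigator judges health under criterion 2 and, under Section 4.1, need not include every eligible person. A nursing mother is also unlikely to accept two stays of this length, and the stays themselves largely prevent direct nursing near peak.

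Most of this stands as a limit on reach. The consent form cannot be checked, so the claim has to be conditional on it. Discretion and inconvenience make the event rare, but neither is a rule, and a rare event also makes the exclusion cheap.

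Two stronger readings are tempting, and the documents support neither.

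- A reader might infer that 5b deliberately admits nursing participants, because 5a has already dealt with breastfeeding partners. In 5a those partners are named only to trigger the man's condom use; the bullet on the partner's own contraception does not mention breastfeeding. The parenthesis in 5b can therefore add something for partners. Its likely purpose is to say that nursing does not remove childbearing potential, which fits the refusal of lactational amenorrhoea in Section 10.4. The sentence is ambiguous and is not a permission. The gap rests on the silence of the lists.
- A reader might take everyone still to be randomized as the number at risk. That count includes men and women who are not nursing, so it does not measure reach.

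**Conclusion.** The point holds as a gap in the protocol's own criteria: they do not exclude breastfeeding participants, and the provisions elsewhere only record or report exposure. Unless the consent form adds a restriction, a nursing woman could be dosed without any rule on feeding her infant.

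The size is small and partly unknown. The documents do not say how many participants are nursing, and the number may be zero. Confinement limits direct nursing near peak, and on the half-lives given (mono-exponential decline assumed) about 4% of peak total molybdenum and less than 0.1% of bupropion remain in the mother's plasma at Day 11. The risk to an infant cannot be quantified from these documents, and the plasma fractions should not be read as an estimate of it. The primary pharmacokinetic comparison, the sample size and the SAP analyses are unaffected. The change is worth making because it closes a safety gap at very little cost.

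**What to change.** Add one exclusion criterion to Section 5.2: 'Currently breastfeeding.' Pregnancy need not be added, since criterion 5b already screens it out by serum test. In 5b, limit the parenthesis about breastfeeding females to partners of male participants, so that the two criteria agree.

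The cost is wording only, with no new test, visit or analysis. The downside is possibly a few fewer eligible women at a unit where, according to the amendment summary (Administrative Change Letter 2), women have been hard to recruit. The sex-ratio requirement has since been removed, so this would not breach an enrolment rule.
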